## 11.4 Interim Monitoring and Analyses

No formal interim analysis will be performed during the course of the feasibility study. The TSC will assess the actual recruitment rates and makes decisions on whether to stop the trial based on poor recruitment.

## 11.5 Analysis Plan

Feasibility and overall recruitment rate will be assessed at the opened sites by calculating the total number of patient participants randomised per month and the ratio of successful recruitment to eligible patients approached. Furthermore, observed recruitment rates, by site and overall, will be summarised along with a 95% confidence interval.

**IRAS Ref: 271885** Page 51 of 89

Much of the analysis will be performed using summary statistics and graphics. No formal assessments of efficacy, cost or safety across treatment arms will be made. All presentations of the data will take the form of summary analysis and graphical representations. Continuous data shall be presented using measure of median (interquartile ranges), whereas categorical data shall be presented in terms of frequencies of counts and associated percentages.

Primary and secondary outcomes will be compared between the two arms using a chisquared or Fisher's exact test.

All analyses shall be carried out on an intention to treat basis, retaining all patient participants in their initially randomised groups irrespective of any protocol deviations. The exception to this is the analysis of safety data which shall be analysed on the safety set which is defined by the type of arthroplasty that patients receive.

Feasibility of the study will be measured on the ability of the study to meet the recruitment targets and Stop/go criteria are defined on this basis.

Following 6 months of active recruitment, a target of 40 patient participants is set. If recruitment is  $\geq$  80% of this target ( $\geq$ 32 patients) a future full study can be considered feasible. If the observed recruitment rate is between 50% and 80% of the target (20-31 patients) then a future full study could potentially go ahead only if satisfactory measures can be taken to improve recruitment. Such measures must be realistic and have support of the study sponsor. If recruitment is less than 50% of the anticipated rate ( $\leq$ 19 patients) than the study won't be considered feasible to evolve into a full one in the future.

In addition, in order for the study to be considered feasible, it should not demonstrate any serious issues related to randomisation process, patient participant retention and/or protocol deviations.

Statistical analyses will be performed using a suitable recognised statistical software such as Stata v15 or above, R v3.3.0 or above and SAS v9.3 or above.

A separate analysis plan including the above details and a shells document containing dummy figures and table shells will be provided before the final analysis.

**IRAS Ref: 271885** Page 52 of 89

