## 4 TRIAL DESIGN

# 4.1 Overall Design

HipHOP is a randomised feasibility study in preparation for a phase III, two arm, blinded, multi-centre, pragmatic randomised controlled trial comparing fully cemented and hybrid total hip arthroplasty in patients undergoing total hip arthroplasty.

This feasibility study will have both quantitative and qualitative elements, referred to as Workstream 1 and Workstream 2 respectively.

The Workstream 1 population is patients undergoing a primary total hip arthroplasty. Patient participants will be recruited from three sites and randomised to the two arms of the trial to receive either a fully cemented hip implant, or a hybrid hip implant. A total of 40 patient participants will be randomised on a 1:1 ratio. Recruitment will take approximately 6 months. Patient participants will be blinded to the type of hip prosthesis received. All possible efforts will be made for the patient participants to remain blinded until their 3-6 month post-operative PROMS are completed to ensure the integrity of the outcomes reporting. Staff collecting outcome data will also be blinded where possible (see section 9).

There are no exclusions to the *size* of socket used in the procedure. Deviation from the socket *type* that is selected at random is allowed, but only if it is established during surgery that the randomised socket type is unsuitable.

Comparison of the types of implant will be made using data collected using Patient Reported Outcome Measures. A healthcare resource use survey will also be provided to patients to complete. Data from this survey will be used to determine if a cost analysis will be possible in a larger phase III study.

Participants would have reached the end of their study involvement once their 3-6 month post-operative visit has been completed.

The Workstream 2 population is patients who both accepted or declined participation in Workstream 1, consultant orthopaedic surgeons and other health professionals.

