#### 7.3 Randomisation

Randomisation shall occur pre-operatively once the patient has been deemed eligible for the study, provided written informed consent and their baseline procedures completed. The randomisation sequence is pre-determined by LCTC, see section 11.1 for further details.

**IRAS Ref: 271885** Page 39 of 89

The randomisation will be processed using REDCap, a commercially available on-line research database system, and will be processed by the research team at the recruiting site. It should be completed as soon as possible for the purposes of operation list planning and implant procurement, and must be no later than the day prior to surgery. The only caveat to this deadline is for patients who will not be consented until the day of their surgery, in which case randomisation should be completed as soon as it is possible to do so.

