## 11 STATISTICAL CONSIDERATIONS

#### 11.1 Method of Randomisation

Once consent has been obtained, participants shall be randomised on a 1:1 basis including the participating site as a stratification factor. Randomisation lists shall be produced by the trial statistician at the LCTC using randomly permuted blocks with separate lists created for each stratification factor. Lists shall be created using Stata (version 15 or above) using the add-on package 'ralloc'.

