#### 11.2 Outcome Measures

#### **11.2.1 Primary**

- 1. Recruitment rate will be measured by the:
  - i. Total number of patient participants randomised per month, and
  - ii. Ratio of successful recruitment to eligible patients approached.

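### Section 11.5 orders between-arm chi-squared or Fisher tests that its preceding paragraph rules out, and that do not fit the primary outcome or the numeric secondary outcomes

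*Protocol*

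**What the plan says.** Section 11.5 gives two instructions in consecutive paragraphs.

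- The first paragraph says: "No formal assessments of efficacy, cost or safety across treatment arms will be made". It continues: "All presentations of the data will take the form of summary analysis and graphical representations". Continuous data are to be shown as median and interquartile range, categorical data as counts and percentages.
- The next paragraph says: "Primary and secondary outcomes will be compared between the two arms using a chisquared or Fisher's exact test". It makes no exception by type of outcome.

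Section 11.2.1 defines the primary outcome as recruitment, in two parts: the number randomised per month, and the "Ratio of successful recruitment to eligible patients approached". Section 11.5 opens by saying how these will be assessed: by site and overall, with a 95% confidence interval.

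The secondary outcomes in section 11.2.2 are mixed. Some are numeric: change in OHS, FJS, WPAI-SHP and SAPS, the EQ-5D-5L, length of stay in hours, operation time in minutes, age and BMI. Others are binary: unblinding, withdrawal, revision, re-operation for infection, treatment cross-over, and intra-operative and postoperative complications.

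Section 11.3 bases the target of 40 on estimating variance, not on detecting a difference. It plans a single longitudinal model for the PROMs, confidence intervals for the variances, and an ICC.

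**The concern.** An analyst cannot obey both paragraphs of section 11.5. Secondary outcomes include efficacy (PROMs) and safety (revision, infection, complications). Testing them between arms is a formal assessment of the kind just excluded. Nothing in the text says which paragraph prevails. The section closes by saying that the separate analysis plan will include these details, so the conflict is set to carry forward.

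The named tests also fit only some of the outcomes. They have no meaningful form for the primary outcome, and they need categories that the protocol does not define for the numeric secondary outcomes.

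At stake is the reporting. Followed literally, the sentence yields between-arm p-values from a feasibility study that was not sized for them. A non-significant result could be read as showing that the implants perform alike, and a chance significant one as favouring an implant.

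**Working it through.** **The plan's own figures.** The only numeric targets tied to the primary outcome are the recruitment rate and the progression cut-offs.

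- Rate (section 11.3): 40 / (3 sites × 6 months) = 2.22 per site per month, as stated.
- Cut-offs (section 11.5): 0.8 × 40 = 32 and 0.5 × 40 = 20, as stated.

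Neither uses a between-arm test.

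**Primary outcome, recruited over approached.** Section 7.3 fixes when the arm is assigned: "Randomisation shall occur pre-operatively once the patient has been deemed eligible for the study, provided written informed consent and their baseline procedures completed". Eligible patients who are approached and decline are in the denominator but never receive an arm, so the ratio cannot be computed by arm. If only randomised patients are kept, the table of arm by randomised (yes/no) has an empty column:

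| Split of 40 | Table (yes, no) | Odds ratio | Fisher p |
|---|---|---|---|
| 20 / 20 | 20, 0 v 20, 0 | undefined | 1.0 |
| 21 / 19 | 21, 0 v 19, 0 | undefined | 1.0 |
| 22 / 18 | 22, 0 v 18, 0 | undefined | 1.0 |

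The answer is the same whatever the split.

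**Primary outcome, number per month.** This count can be split by arm. Under section 11.1, however, "participants shall be randomised on a 1:1 basis including the participating site as a stratification factor", using permuted blocks. The split therefore reflects the allocation lists and says nothing about feasibility.

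**Numeric secondary outcomes.** Chi-squared and Fisher tests compare category frequencies. The protocol gives no categories for PROM change, hours, minutes, age or BMI, and section 11.5 itself summarises continuous data by median and interquartile range. The tests do not fit these outcomes as defined.

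**Binary secondary outcomes.** Here the tests can be computed, but they carry little information. Inputs: 40 patients at 1:1, so 20 per arm. Assumed because the protocol gives neither: two-sided 5% level, and the event rates below. Exact power is the sum of Bin(x; 20, p1) × Bin(y; 20, p2) over all tables (x, y) with Fisher p ≤ 0.05.

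| Assumed rates | Exact Fisher power |
|---|---|
| 5% v 15% | 7% |
| 5% v 20% | 17% |
| 10% v 30% | 24% |
| 5% v 25% | 30% |

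With no events in one arm, 4/20 v 0/20 gives p = 0.106 and 5/20 v 0/20 gives p = 0.047. At least five events against none are needed to reach nominal significance.

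**The case against.** The strongest reply is that the study's conclusion does not depend on this sentence. Feasibility is decided on the number recruited (32 or more, 20 to 31, 19 or fewer) and on the absence of serious problems with randomisation, retention or deviations. Section 11.5 already states a workable primary analysis. This stands, and it limits the severity.

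Four stronger readings are tempting, and the documents do not support them.

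- **All between-arm testing is forbidden.** A reader might infer this from the first paragraph. The sentence on formal assessments covers only efficacy, cost and safety. Section 11.2.2 sets out unblinding and withdrawal by arm, and testing those would not breach it. The wider obstacle is the next sentence, which confines all presentations to summaries and graphics.
- **The test is impossible for the whole primary outcome.** That is exact only for the recruited/approached ratio. The monthly count can be split by arm, though uninformatively.
- **Section 4.1 adds a second contradiction.** It says "Comparison of the types of implant will be made using data collected using Patient Reported Outcome Measures". It names no test and is compatible with a descriptive comparison.
- **A chance positive is likely.** A reader might count about 20 items in section 11.2.2 and compute 1 − 0.95^20 = 0.64. That count includes about nine numeric items to which the tests do not apply, and it takes each test at a true 5% size. About nine binary items remain. With 20 per arm, Fisher's true size is 0.2%, 1.2% or 2.5% at assumed common event rates of 5%, 10% or 30%. Nine independent tests then give 1 − (1 − 0.002)^9 ≈ 2% up to 1 − (1 − 0.025)^9 ≈ 20%.

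It could also be said that test details belong in the analysis plan. That does not help here: the protocol states an instruction, and it conflicts with the paragraph above it.

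**Conclusion.** The point holds as an internal contradiction and a misapplied method. It should be fixed, but it does not threaten the study's conclusion.

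Three parts rest on the text alone: the clash with the preceding paragraph for efficacy and safety outcomes, the absence of any by-arm form for the recruited/approached ratio, and the misfit with numeric outcomes. The size of the harm is illustrative. Power of 17% (5% v 20%) and 24% (10% v 30%) depends on assumed event rates, a two-sided 5% level and 20 evaluable patients per arm. The harm is confined to p-values that could be over-read. The target of 40, the rate of 2.22 and the stop/go cut-offs are untouched.

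**What to change.** Delete the sentence in section 11.5 and replace it with:

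> Primary outcomes will be summarised overall and by site with 95% confidence intervals. Secondary outcomes will be summarised descriptively by arm, without between-arm hypothesis tests; the longitudinal model, variance estimates with confidence intervals and ICC in section 11.3 are reported as planned.

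The last clause is needed so that the new text does not conflict with section 11.3. Optionally, add to section 4.1 that the PROM comparison is descriptive. If the team does want tests for categorical process outcomes such as withdrawal or unblinding, it should name those outcomes and amend the summaries-only sentence to match.

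The cost is a change of wording in one paragraph, carried into the analysis plan if that repeats the sentence. It needs no new data, alters no stated number and reduces the analysis work.

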#### Quantitative questions:

The most important of these is to determine whether it is possible to recruit an adequate number of patients within a suitable timeframe to the study. A number of recent national orthopaedic RCTs have suffered from low recruitment rates. It is

**IRAS Ref: 271885** Page 26 of 89

therefore important to identify realistic recruitment rates prior to engaging upon the full study.

The primary outcome measure for the full study will be a patient-reported functional outcomes questionnaire. In order to perform accurate sample size calculations, we need to know the variability (standard deviation) and loss to follow-up rate for the proposed method of collection of these scores.

One concern with comparative surgical trials is that during surgery, the surgeon may decide to use the alternative method due to some new or unforeseen intraoperative surgical finding. This would potentially skew the trial results and the rate of this occurrence is unknown. Whilst we will analyse the functional results on an intention to treat basis, we will measure the rate of treatment cross-over during surgery. During the feasibility study, the opportunity will also be used to survey potential sites and surgeons for their willingness to be involved in a future trial and to estimate the number of patients that may be included.

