## Reporting requirements decision tree:

**IRAS Ref: 271885** Page 55 of 89

Table C	: Adverse Events of Special Interest (in alphabetical order).
Event	
1.	Cerebrovascular accident
2.	Deep infection
3.	Deep Vein Thrombosis
4.	Dislocation of hip (subluxation or dislocation of joint)
5.	Fracture around joint including femoral shaft perforation or fracture, calcar fracture, trochanteric fracture, acetabular (fracture or perforation) or pelvic fracture (intraoperative)
6.	Fracture around joint including trochanteric avulsion, femoral or acetabular or pelvic fracture (postoperative)
7.	Haematoma
8.	Heterotopic ossification of joint leading to pain or stiffness (periarticular calcification or ossification)
9.	Loosening of implants (early or late, change in position of implants, subsidence of implants or tissue reaction/osteolysis)
10.	Myocardial infarction
11.	Nerve injury (temporary or permanent nerve damage including femoral, obturator, peroneal, sciatic)
12.	Organ/Multiorgan failure
13.	Pain from joint
14.	Pneumonia
15.	Pulmonary Embolism
16.	Revision surgery
17.	Superficial infection
18.	Vascular injury (including iliac, obturator and femoral artery injury)
19.	Wear or fracture or fatigue fracture of implants

**IRAS Ref: 271885** Page 56 of 89

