## 12.8.3 Timeframe categories

- Intra-operative: AE occurred between the start and end of the total hip arthroplasty operation, i.e. knife to skin, to when the application of the dressing is completed.
- Early post-op: AE occurred any time after the end of the total hip arthroplasty operation, up to and including 6-weeks post-operation (i.e. 42 days, with the day of the operation being day 0).
- Late post-op: AE occurred any time in or after the seventh week post-operation (i.e. from and including day 43, with the day of the operation being day 0).

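### Grouping safety data by implant received would count an intra-operative event that forces a socket change against the fallback implant

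*Protocol*

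**What the plan says.** Section 11.5 makes intention to treat the default, "retaining all patient participants in their initially randomised groups irrespective of any protocol deviations". Safety data are the single exception and are analysed on a "safety set which is defined by the type of arthroplasty that patients receive".

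Section 4.1 allows departure from the randomised socket type "but only if it is established during surgery that the randomised socket type is unsuitable". Section 2.2 (Quantitative questions) gives the mechanism: "the surgeon may decide to use the alternative method due to some new or unforeseen intraoperative surgical finding".

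The safety reporting period opens at the first incision (section 12.7.2). The intra-operative category in section 12.8.3 covers any case where the "AE occurred between the start and end of the total hip arthroplasty operation", and it is not divided at a socket change. Table C, item 5, lists among the AESIs "acetabular (fracture or perforation) or pelvic fracture (intraoperative"). AESIs are reportable from Clavien-Dindo grade 3 (sections 12.3 and 12.8.1).

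Intra-operative and post-operative safety is secondary objective 5, and the incidence of cross-over is objective 6 (section 2.3). The matching outcomes in section 11.2.2 are 4.vi (cross-over) and 4.vii (intra-operative complications above grade III).

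**The concern.** For later events such as loosening or dislocation, grouping by the implant in place is a sensible convention. It works less well for events that happen before the final implant is chosen. In this trial a permitted cross-over arises from what the surgeon meets during the operation, and one thing that can be met is a complication of the attempt itself. In that case the outcome being measured decides which group the patient belongs to. The event moves to the fallback implant, and the implant whose attempt led to the event loses both the event and the patient.

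At stake is the descriptive picture of intra-operative safety by implant. Section 2.2 already recognises that cross-over could distort the results and protects the functional outcomes by intention to treat. The safety rule removes that protection at the point where cross-over and outcome can be most closely linked.

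**Working it through.** The protocol states no complication rate and calls the cross-over rate unknown, so there is no figure of the plan to reproduce. The check has two parts: what the rule does to one patient, and how much the table changes.

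**One patient.** Suppose the patient is randomised to hybrid, the acetabulum fractures while the uncemented socket is being inserted, and the surgeon changes to a cemented socket.
- Section 4.1 permits the change, because the reason was established during surgery.
- Sections 12.7.2 and 12.8.3 count the fracture as intra-operative, and Table C item 5 makes it an AESI (reportable if grade 3 or above).
- Section 11.5 places the patient in the group of the arthroplasty received. On the natural reading this is the final implant, cemented.
- No section assigns an event that precedes the change to the socket being attempted.

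The mirror case, cemented to hybrid, works in the same way.

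**The table.** The inputs are 40 patients randomised 1:1 (section 4.1), so about 20 per arm. Event and switch counts are assumptions, and switches are taken in one direction only. Let *h* and *c* be the events among patients randomised to hybrid and to cemented, and *s* the number of hybrid events that force a switch. By randomised arm the proportions are *h*/20 and *c*/20. By implant received they are (*h* − *s*)/(20 − *s*) and (*c* + *s*)/(20 + *s*).

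| h, c, s (assumed) | By randomised arm: hybrid v cemented | By implant received: hybrid v cemented |
|---|---|---|
| 1, 0, 1 | 1/20 (5.0%) v 0/20 | 0/19 (0%) v 1/21 (4.8%) |
| 2, 0, 1 | 2/20 (10.0%) v 0/20 | 1/19 (5.3%) v 1/21 (4.8%) |
| 2, 0, 2 | 2/20 (10.0%) v 0/20 | 0/18 (0%) v 2/22 (9.1%) |
| 2, 2, 1 | 2/20 (10.0%) v 2/20 (10.0%) | 1/19 (5.3%) v 3/21 (14.3%) |
| 2, 2, 2 | 2/20 (10.0%) v 2/20 (10.0%) | 0/18 (0%) v 4/22 (18.2%) |

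In rows 1 and 3 the direction reverses. In row 2 the difference almost disappears. In rows 4 and 5 a difference appears where there was none. None of these contrasts is statistically significant: in row 5 the Fisher's exact p is 1.0 by randomised arm and 0.11 by implant received.

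**A range.** Take a common risk *q* = 5% in each arm, so one expected event per arm, and let a fraction *f* of hybrid-arm events force a switch. Using expected counts, the as-received proportions are (1 − *f*)/(20 − *f*) and (1 + *f*)/(20 + *f*).
- *f* = 0.25: 0.75/19.75 = 3.8% v 1.25/20.25 = 6.2%.
- *f* = 1: 0/19 = 0% v 2/21 = 9.5%.

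With no switches, the two tabulations agree.

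**The case against.** **As-received safety sets are conventional, and safety here is descriptive.** Both are true. Section 11.5 says no formal assessment of safety across arms will be made, although the same section then plans chi-squared or Fisher's exact tests of the secondary outcomes between arms. A descriptive table can still mislead, and the convention fits post-operative events much better than events that cause the switch.

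**The reach into outcome 4.vii is small.** This stands. Outcome 4.vii counts only severity above grade III, which on Table D means grades 4 and 5. A fracture managed by using another socket would not exceed 3b for that reason alone. It is also unsettled whether 4.vii is safety data: section 11.2.2 lists it with clinical and patient-reported data, and section 7.10 describes safety through post-operative events, whereas objective 5 names intra-operative safety.

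**Cross-over need not follow a complication.** This also stands. The protocol speaks of a finding and of unsuitability. A change made for another reason moves a patient but no event.

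**The randomised arm is not always the technique attempted.** A surgeon may judge the randomised socket unsuitable before trying it. Grouping by randomised arm alone would then charge later events to a technique that was never used. For this reason the remedy must show both groupings and the sequence of events.

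**It can be left to the analysis plan.** Only in part. Section 11.5 itself fixes the as-received grouping and says that the separate analysis plan will include these details, so that plan would start from this rule.

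**Conclusion.** The point holds in a limited form. As section 11.5 is written, an intra-operative AESI that arises during the attempt at the randomised socket and leads to the other socket is counted against the other implant, and the patient leaves the denominator where the event happened. Each such case takes about 5 percentage points out of one group (1/20) and adds between 4 and 5 to the other (1/21 or 1/22), so one or two could remove or reverse an apparent difference. This rests on assumed counts, on about 20 patients per arm, and on reading the implant received as the final one, since the protocol does not define the term for a socket that is tried and exchanged. If no cross-over follows a complication, no event is misattributed. The effect falls mainly on AESIs of grade 3 or above.

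A reader might infer two further consequences that the protocol does not support.
- The first is that the comparison of serious adverse device effects by implant type in section 12.10 is distorted as well. That rule does not refer to the safety set in section 11.5, and section 12.6 assigns relatedness separately to stem, socket and cement.
- The second is that biased complication rates pass into the design of the full trial. The quantitative inputs named in sections 2.2 and 11.3 are recruitment, variability of the patient-reported scores, loss to follow-up or retention, cross-over and intraclass correlation. Complication proportions are not among them.

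**What to change.** Amend section 11.5 as follows:
- Tabulate intra-operative complications and AESIs by randomised arm as well as by implant received.
- Keep the as-received set for post-operative events.
- List each crossed-over patient with the randomised implant, the implant received, the reason for the change and any intra-operative event. State whether the event came before or after the change, or before the randomised socket was attempted.

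The cost is small: a sentence or two in section 11.5 and one extra table or listing, with a footnote to explain the two groupings. Changes of implant type are already collected (section 7.4). Timing relative to the socket change is not a category in section 12.8.3, so one additional CRF item may be needed.
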